### 6.5 Blood Collection

Experienced nurses will obtain a venous blood specimen (approximately 2-3 mL of blood) by venipuncture (preferably) or by heel stick if venipuncture unsuccessful at Visit 1 (pre-vaccination and Visit 2 (post-vaccination) for cytokine and biomarker assays.

## 6.6 MRI/Ultrasound Imaging

Using MRI, a non-invasive imaging method that does not use radiation, we will 1) assess intestinal wall thickness, 2) lymph nodes and 3) intestinal motility patterns that may be associated with an increased risk for intussusception. The MRI will be done at Visit 1 just prior to the ultrasound and rotavirus vaccination and similarly at Visit 2 to ascertain for any changes in these three parameters between the two exams. A trained MRI technician will conduct the procedures in accordance with standard practice.

At recruitment/enrollment, parents will be informed that to be included in the study, they will be asked to keep their infant NPO for approximately 3 hours prior to Visit 1 and Visit 2 appointment time. Parents will have a reminder call the day prior to each visit to confirm the study time and remind them to keep the infant NPO. Research staff will meet the parent at the Welcome Center and escort the parent and child to the CCHMC Imaging Research Center (IRC). The infant will not be sedated for the MRI; rather, the infant will be fed and swaddled. All images will be obtained on a 1.5T Philips MRI scanner located in the IRC after appropriate metal screening and ear protection (ear plugs and MiniMuffs™ (Natus Medical Incorporated, San Carlos, California)).

The infants will not receive intravenous contrast. However, they will receive enteric contrast by mouth to optimally distend the small bowel and therefore improve image quality. Thirty minutes prior to imaging, each subject will be fed 20 mL/kg of a 3:1 mixture of VoLumen (Bracco Diagnostics) slowly over about 25 minutes. The infants will then be imaged supine in an appropriately sized coil such as a cardiac coil. The approximate time in the MRI to obtain the images needed will be 30-60 minutes. Once started the MRI procedure may be stopped if the baby becomes upset. Once calm, the scan can be repeated as necessary. If a clinically concerning finding is found on the images, the radiologist will notify the PI who will contact the parents and primary care physician.

After completion of the MRI, an ultrasound of the abdomen will be done. The non-invasive ultrasound will be done to 1) assess intestinal wall thickness and 2) lymph nodes that may be associated with an increased risk for intussusception. The ultrasound will be done at Visit 1 just after the MRI and prior to rotavirus vaccination and similarly at Visit 2 to ascertain for any changes in these two parameters between the two exams. A trained ultrasound technician will conduct the procedures in accordance with standard practice. The ultrasound will take up to 30 minutes to complete.

## 6.7 Rotavirus Vaccine Administration

No restrictions are placed on the infant's feeding before or after receipt of rotavirus vaccine (except as needed for the MRI). Documentation of whether the child is being breastfed and/or type of formula will be collected. While the efficacy of the rotavirus vaccine series is similar among breastfed and nonbreastfed infants, breastfeeding could potentially be related to outcome so we will document feeding practice at each visit and daily on the memory aid. Even though rotavirus vaccine can be administered to infants with minor acute illness (e.g., mild gastroenteritis or mild upper-respiratory tract infection, with or without fever), both minor and major acute illnesses will be exclusion criteria, as these conditions could interfere with our outcome measures (gastrointestinal motility and anatomy and cytokine responses).

## 6.8 Reactogenicity Assessment

Reactogenicity will be assessed for both groups for fourteen days after vaccine receipt (Days 0-14) and recorded by the parent/legal guardian on a provided memory aid. The events will include fever, fussiness and gastrointestinal symptoms such as vomiting and diarrhea (number of stools per day and looser than normal). Parents will be instructed not to take temperature after bundling and how to distinguish vomiting from normal spitting. Data will be collected using review of memory cards with the parent. We have found this to be accurate, simple and acceptable to the parents of young infants. The following reactogenicity signs/symptoms will be collected:

- Diarrhea: defined as 3 or more episodes of looser-than-normal stools in 1 day
- Vomiting: 1 episode of vomiting (forceful expulsion of partially digested milk/food) in 1 day
- Fever: axillary temperature  $\geq 99.5$  degrees F (measured once daily or more frequently if perceived fever)
- Hematochezia: maroon stools or any evidence of blood in the stool-black and tarry stools or frank red blood
- Irritability

The following grading system will be used in evaluating the fever and systemic events during Days1-14 following vaccination:

Reaction	Mild (Grade 1)	Moderate (Grade 2)	Severe (Grade 3)
Fever (axillary)	$\geq 99.5^{\circ}\text{F}$ to $\leq 100.4^{\circ}\text{F}$	$>100.4^{\circ}\text{F}$ to $\leq 102.2$	$>102.2^{\circ}\text{F}$ and higher
Diarrhea	3 looser than normal stools/ day	4-5 loose stools/ day	$> 6$ loose stools/ day
Vomiting	1 episode of vomiting/ day	2 episodes of vomiting/ day	$\geq 3$ episodes of vomiting/ day
Irritability	Crying more than usual	Some interference with normal activity	Significant interference with normal activity
Hematochezia	Any stools that are black and tarry; maroon in color; or, frank red blood-each episode will be reported to infant's medical provider immediately		

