#### 3.3 Primary and Exploratory Objectives

Primary Objectives:

- 1) to examine the effects of RV1 and RV5 with or without other routine immunizations on gastrointestinal anatomy
- 2) to assess the feasibility of conducting a larger scale study

Exploratory Objectives:

- 1) to examine the effects of RV1 and RV5 with or without other routine immunizations on gastrointestinal motility
- 2) to examine the effects of RV1 and RV5 with or without other routine immunizations on blood and stool cytokines and inflammatory responses, including clinical reactogenicity events
- 3) to assess patterns and level of vaccine virus shedding after RV1 and RV5
- 4) to provide preliminary data assessing associations with the pattern of rotavirus vaccine strain (RV1 and RV5) shedding in the stool and blood, stool cytokine responses, and the anatomy and/or functional motility of the small intestine; and examine other factors such as maternal antibody, breast milk antibody, and human blood group antigens to see if these factors modify these responses
- 5) to compare MRI and ultrasound imaging

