Recruitment and enrollment will occur prior to the first study visit. There will be three scheduled study visits after recruitment/enrollment. . Infants will be randomized to either RV1, RV1 plus other immunizations, RV5 alone, or RV5 plus other immunizations. Visit 1 (day 0) will include blood, saliva, stool and breast milk collection . The MRI and ultrasound will be performed prior to vaccination. Children will receive the immunizations to which they are randomized. Imaging personnel and parents will be blinded to rotavirus vaccine type; they will be informed about other vaccines administered. A second MRI and ultrasound will be performed at Visit 2 (day 5) and blood and stool samples collected. Parents will be unblinded at the completion of Visit 3 (day 14). Arrangements will be made to get remaining doses of same rotavirus vaccine. Daily stool samples will be collected at home during the 15 day study period (on vaccination day 0 and for next 14 days). A memory aid will be completed to collect reactogenicity data on days 0 and for the next 14 days. Remaining stools and reactogenicity data from parents will be collected at Visit 3. **See Appendix 1 for detailed description of visits and timeline.**

We will assess blood and stool cytokine responses and intestinal anatomy and motility after rotavirus vaccination by comparing pre-vaccination with post-vaccination responses in the study infants. Cytokines and intestinal anatomy and motility will be assessed at baseline (Visit 1, the day of vaccine receipt) and 5 days after vaccination (Visit 2). For both blood and stool, the following cytokines will be tested: IL-2, IL-6, IL-7, IL-8, IL-15, INF- $\gamma$  and TNF- $\alpha$ . Additional biomarkers may be studied. The 5 day period post-vaccination was chosen because this time period corresponds with the peak period for intestinal replication of rotavirus vaccine virus for both vaccines.

In order to protect the health of infants, we will provide procedures to facilitate and assure that infants enrolled in the study will receive the routinely recommended vaccines for 2 month old infants which are DTaP, Hib, PCV13, HBV and IPV that will also allow them to get their 4 month vaccines on schedule.

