## 5.3 Study Visits

### Enrollment/Recruitment Visit

- review inclusion/exclusion criteria and medical history
- obtain informed consent
- obtain a release to get medical information from the primary care provider
- collect contact information including the primary care provider of infant and the date of 2 month check up if known
- if refuses study, record refusal reason on screening log
- sample collection instructions
- distribute sample collection supplies
- review MRI and ultrasound prep
- randomize to study group and inform parent of result of all routine vaccines or rotavirus vaccine alone (not specific rotavirus vaccine type)
- schedule visit 1  
give written instructions for Visit 1 to parent (Appendix 5) **Reminder Call 1 (day prior to Visit 1)**
- review sample collection instructions
- review MRI/ultrasound prep  
review time, date and location of Visit 1 **Visit 1 (Day 0-Vaccine Administration)**
- contact information will be reviewed and updated if necessary
- inclusion and exclusion criteria will be reviewed to determine if child still meets criteria for study
- temperature will be recorded prior to immunization; axillary temperature must be <100.4° F prior to administration of vaccines
- breast milk specimen brought from home if mother is breast feeding or can be collected at the visit if needed
- saliva specimen collected for human blood group antigen testing
- baseline stool specimen (brought from home) before receiving the rotavirus vaccine
- MRI to assess intestinal anatomy and motility
- Ultrasound of abdomen to assess intestinal anatomy
- baseline blood specimen for cytokine testing and maternal antibody testing (IgG)
- The Vaccine Information Sheet (VIS) will be provided to parents/guardians for all vaccines administered.
- The study product administrator, who is licensed to administer the vaccine (e.g., MA, LPN, RN, NP, PA, or MD), will orally administer the rotavirus vaccine as indicated in the randomization code
  - if the infant vomits after receiving the vaccine, in accordance with AAP and ACIP recommendations, the vaccine will not be readministered but time of vaccine administration and vomiting will both be documented.

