## **10 RANDOMIZATION, DATA MANAGEMENT, STATISTICAL PLAN**

### **10.1 Randomization Plan**

Upon meeting the inclusion and exclusion criteria, subjects will be randomized to one of the four vaccine groups: 1) RV1 alone, 2) RV5 alone, 3) RV1 with routine immunizations (DTaP, Hib, PCV13, HBV and IPV) or 4) RV5 with routine immunizations. This will be a simple randomization using SAS® PROC PLAN, which uses a random number generator to make assignments. Study statisticians will generate the assignments in advance of any enrollment. After obtaining informed consent, an unblinded research personnel will contact the statistician to obtain a specific subject's assignment. Parents and all study radiologists will be blinded as to which arm the child is randomized to until completion of the study. Parents will learn which rotavirus the child received at the completion of Visit 3. Parents will be informed about the specific other vaccines used in the study. If there is an urgent medical need to unblind during the study, then this can be done by calling the on call study staff.

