#### **a) Descriptive statistics:**

Descriptive statistics will be calculated for all demographic, anthropometric, reactogenicity, serum, image and fecal variables. For continuous variables, five-number (mean, SD, minimum, median, maximum) summaries will be produced. For class (categorical) variables, frequencies and percentages will be reported. Descriptive statistics will be calculated for the entire study population, as well as for each vaccine group at each time point. Investigators will be advised by study statisticians about potential outliers, or data entry issues, based on these summary statistics. To determine whether continuous serum, image and fecal outcomes meet the assumption of a Gaussian (normal) distribution, the Shapiro-Wilk test will be used. Where a significant departure from normality exists, an appropriate transformation of the data will be employed prior to inferential analyses. If transformations are not successful, non-parametric analyses will be used.

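### Fever counts any reading at or above a low cut-off, parents add readings on suspicion, and they know whether routine vaccines were given, so the exploratory with-routine versus rotavirus-alone fever comparison is open to unequal ascertainment

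*Combined protocol and SAP*

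**What the plan says.** **Definition and measurement.** Section 6.8 begins its fever definition with "Fever: axillary temperature" and sets the cut-off at 99.5 F. Temperature is "measured once daily or more frequently if perceived fever", and reactogenicity is "recorded by the parent/legal guardian on a provided memory aid". The grading table in the same section puts 99.5 to 100.4 F in Grade 1. No confirming reading is asked for, and nothing says which reading counts on a day with several.

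**What parents know.** The enrolment visit in section 5.3 includes this step: "randomize to study group and inform parent of result of all routine vaccines or rotavirus vaccine alone (not specific rotavirus vaccine type"). Section 4.1 agrees: "Imaging personnel and parents will be blinded to rotavirus vaccine type; they will be informed about other vaccines administered". Section 10.1 has a sentence pointing the other way, "Parents and all study radiologists will be blinded as to which arm the child is randomized to until completion of the study", yet the same section goes on to say that parents will be informed about the other vaccines used.

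**Planned use.** Exploratory objective 2 in section 3.3 is "to examine the effects of RV1 and RV5 with or without other routine immunizations on blood and stool cytokines and inflammatory responses, including clinical reactogenicity"; fever is one of the outcomes meant. The background text on other routine immunizations (section 2.3) says that outcomes in the two with-routine arms will be compared with those in the rotavirus-alone arms. Section 10.3(a) covers reactogenicity among the variables to be described for each vaccine group: "For class (categorical) variables, frequencies and percentages will be reported". Section 10.3(b) names no inferential test for fever.

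**The concern.** A fever can be recorded only when a temperature is taken. Where one reading above a cut-off makes a case, adding readings can raise the number of cases but never lower it. Here the scheduled reading is common to all arms, but the additional readings depend on the parent's suspicion. A parent who knows that the infant had several injections has more reason to suspect fever than one who knows that only an oral vaccine was given. Masking RV1 versus RV5 does nothing about this, because the knowledge at issue is routine-vaccine status.

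The stake is the interpretation of one exploratory contrast. The background section already expects an inflammatory response to routine vaccines, so a fever excess in those arms would look like confirmation even if part of it came from more frequent measurement. The Power section says that effect sizes will be reported to help develop future studies, so the artefact could be carried into the planning of a later trial.

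**Working it through.** The plan states no fever rate, no reading count and no power, so there is no figure of its own to reproduce. The calculation shows how large the artefact could be when true temperatures do not differ.

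**Inputs from the documents**
- Scheduled readings: one a day on Days 0 to 14 (sections 4.1 and 6.8), so 15. The grading sentence in section 6.8 refers to Days 1 to 14, which would give 14.
- Sample: up to 150 infants allocated 1:1:1:1 (section 4.1), so 150/4 = 37.5 per arm and 75 versus 75 for with versus without routine vaccines.

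**Assumptions, not in the documents**
- The chance p that a reading reaches 99.5 F is 1%, 2% or 5%, the same in all arms.
- Each with-routine infant has 5 extra readings over the period and each rotavirus-alone infant has none.
- The summary is the percentage of infants with at least one qualifying reading over the whole period. Section 10.3 does not say this; it is the natural reading of an infant-level frequency.

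**Independent readings.** P(any fever) = 1 − (1 − p)^m, with m = 15 or 20.

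| p | m = 15 | m = 20 | Gap (points) |
|---|---|---|---|
| 1% | 14.0% | 18.2% | 4.2 |
| 2% | 26.1% | 33.2% | 7.1 |
| 5% | 53.7% | 64.2% | 10.5 |

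**Correlated readings.** Readings on one infant share a baseline temperature, a thermometer and a parent. In a beta-binomial model with within-infant correlation ρ, P(any fever) = 1 − B(a, b + m)/B(a, b), where B is the beta function, a = p(1 − ρ)/ρ and b = (1 − p)(1 − ρ)/ρ.

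| p | ρ = 0.1: m = 15, m = 20, gap | ρ = 0.3: m = 15, m = 20, gap |
|---|---|---|
| 1% | 8.8%, 10.3%, 1.6 | 5.0%, 5.6%, 0.6 |
| 2% | 16.8%, 19.7%, 2.8 | 9.8%, 10.9%, 1.1 |
| 5% | 37.2%, 42.5%, 5.3 | 22.9%, 25.3%, 2.3 |

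**Sensitivity, independent readings, p = 2%**
- Days 1 to 14 only, 14 versus 19 readings: 24.6% versus 31.9%, a gap of 7.2 points. The choice of window hardly matters.
- Rotavirus-alone infants also get 3 extra readings, 18 versus 20: 30.5% versus 33.2%, a gap of 2.75 points. The artefact depends on the difference in counts, not on extra readings as such.
- One extra reading gives 27.6% versus 26.1% (1.5 points); ten give 39.7% versus 26.1% (13.5 points).

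**Scheduled reading only.** With equal completeness, m = 15 in every arm. At p = 2% both groups show 26.1% and the gap is zero.

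For scale, one infant is 1/37 = 2.7 points in a single arm and 1/75 = 1.3 points in the pooled comparison.

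**The case against.** **Fever is exploratory and descriptive.** Section 10.3(b) specifies analyses for imaging, shedding and cytokines, not reactogenicity, and this is a pilot without a power calculation. This stands. It limits the point to how a descriptive table is read.

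**The grades contain much of the problem.** A stray borderline reading is Grade 1; Grades 2 and 3 lie above 100.4 F. This stands, and is why the concern is mainly about Grade 1.

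**Size and direction are assumed.** A reader might infer that the with-routine arms are certain to show inflated fever, or that a 5 to 10 point artefact is to be expected. The documents do not support either. They give no reading counts. Some extra readings will find real fever, which is detection and not bias. Exclusion criterion 12 (section 4.3) does not exclude infants whose caretaker might give an antipyretic after vaccination to reduce a fever, so the same suspicion could lead to treatment and lower later readings. Within-infant correlation cuts the gap to between 0.6 and 5.3 points.

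**There are controls on measurement quality.** Parents receive a thermometer, demonstrate its use at Visits 1 and 2, are told not to measure after bundling, and have the memory aid reviewed at calls and visits. These should reduce p. They do not equalise the number of readings. The Appendix 2 benchmark counts days with a temperature, not readings per day. The memory aid is not in the documents, so it may already mark a scheduled reading.

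**Using only the scheduled reading would miss brief fevers.** If routine vaccines do cause fever, those misses would fall mainly in the with-routine arms. This stands, and is a reason to show both definitions.

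**Conclusion.** The concern holds as a risk of differential ascertainment in one exploratory contrast. The rule allows reading counts to differ with parental suspicion, parents know routine-vaccine status, the contrast is planned, and nothing in the plan accounts for reading counts. More recorded fever in the with-routine arms is the likely direction, not an established one.

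Under the assumptions above, with 5 extra readings and p from 1% to 5%, the spurious gap is about 4 to 10 points for independent readings and about 0.6 to 5 points with within-infant correlation of 0.1 to 0.3. In the correlated case that is roughly zero to four infants out of 75.

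It would be wrong to extend this to the whole trial. RV1 versus RV5 at the same routine-vaccine status is protected by masking of the parents, apart from any change in measuring prompted by a true difference in symptoms. The primary MRI outcome does not depend on temperature readings. The sentence in section 10.1 that parents are blinded to arm does not remove the problem, since sections 4.1 and 5.3, and section 10.1 itself, say that they are told about the other vaccines.

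**What to change.** 1. Mark one scheduled daily reading on the memory aid, taken at about the same time each day, and record every other reading with its time. Parents stay free to take extra readings.
2. In section 10.3, state that between-arm fever comparisons will show fever by grade on the scheduled reading beside fever by grade on any reading, with the number of readings per infant-day by arm.
3. State in advance that a difference on any reading will be interpreted as a vaccine effect only if the scheduled-reading result agrees in direction or reading counts are similar between arms.
4. Reconcile the parent-blinding sentence in section 10.1 with sections 4.1 and 5.3, and Days 0 to 14 with Days 1 to 14 in section 6.8.

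The cost is one memory-aid column and one table. The scheduled-reading table will miss brief fevers, but these remain visible in the any-reading table. If data are already collected, report readings per infant-day by arm where they were recorded; otherwise state the limitation beside the fever results.

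### Section 6.8 leaves a day with exactly 6 loose stools without a severity grade, and grades Days 1-14 although reactogenicity is collected on Days 0-14

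*Combined protocol and SAP*

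**What the plan says.** Section 6.8 sets the event threshold: "Diarrhea: defined as 3 or more episodes of looser-than-normal stools in 1 day". Its grading table gives Grade 1 as "3 looser than normal stools/ day" and Grade 2 as "4-5 loose stools/ day". Grade 3 is printed with a strict inequality, more than 6 per day.

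The same section gives two time windows. Collection: "Reactogenicity will be assessed for both groups for fourteen days after vaccine receipt (Days 0-14". Grading: the "grading system will be used in evaluating the fever and systemic events during Days1-14 following vaccination".

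Sections 3.4 and 4.1 also collect reactogenicity from Day 0, and the Appendix 1 schedule marks reactogenicity and axillary temperature on every day from 0 to 14. Clinical reactogenicity belongs to exploratory objective 2 (section 3.3). Section 10.3 plans descriptive statistics for reactogenicity variables overall and by vaccine group, with frequencies and percentages for categorical variables. No section says how to treat an event that has no grade, or an event on Day 0.

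**The concern.** A severity scale should give every qualifying event exactly one grade, and should cover the period over which events are collected. Section 6.8 does neither for diarrhoea. The gap lies on the moderate/severe boundary. A 6-stool day would drop out of both the Grade 2 and Grade 3 counts, or whoever codes the data would have to choose a grade, perhaps after seeing the results.

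The second mismatch removes the vaccination day from grading without a stated reason. At stake is the completeness of any summary by grade. Because this is a pilot meant to inform a larger study, there is also a chance that the scale is carried forward uncorrected.

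**Working it through.** There is no sample size, power or alpha to reproduce. The check applies the printed rules literally.

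**Step 1: diarrhoea.** Inputs are the section 6.8 event threshold (3 or more) and the three grade cells.

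| Loose stools in the day | Event? | Grade as printed |
|---|---|---|
| 3 | yes | 1 |
| 4 | yes | 2 |
| 5 | yes | 2 |
| 6 | yes | none |
| 7 or more | yes | 3 |

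Six is the only count at or above the threshold with no grade. No count has two grades.

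**Step 2: the other numeric rows of the table.** Vomiting is graded 1, 2, and 3 or more, so every count from 1 up has one grade. Fever runs from 99.5 to 100.4°F, above 100.4 to 102.2°F, and above 102.2°F. Taken in steps of 0.1°F from 99.5 to 103.9°F, every value has exactly one grade. The gap is confined to diarrhoea.

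**Step 3: the windows.**
- Collected days: 0 to 14, which is 14 − 0 + 1 = 15 days.
- Graded days: 1 to 14, which is 14 − 1 + 1 = 14 days.
- Difference: Day 0 only; 1/15 = 6.7% of collected days.

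The 6.7% is a share of days, not of events. The collection sentence also calls Days 0-14 fourteen days, although that range holds fifteen, which is a further reason to restate the windows.

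**Step 4: does closing the gap work?** Extending Grade 2 to 4-6 and leaving Grade 3 at more than 6 gives each count of 3 or more one grade. So does keeping Grade 2 at 4-5 and starting Grade 3 at 6. The arithmetic does not favour either one.

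**The case against.** The best defence is that little depends on the grade. The plan specifies no graded table, no endpoint based on grade and no test of reactogenicity; the inferential analyses in section 10.3 concern imaging, shedding and cytokines. Withdrawal (section 4.4) and VAERS reporting (section 11.2) do not use these grades. Stool counts and temperatures are collected, so a numeric grade can be assigned later. All of this stands, and it limits the point to summaries by grade.

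The strict inequality may be a slip of sign, or an underline lost when the PDF was read. That cannot be fully excluded, but the greater-than-or-equal sign survives in the fever and vomiting rows of the same table, so the cell has to be taken as printed.

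Day 0 might have been left out on purpose. Every arm fasts, takes oral contrast and has blood drawn that day; section 11.1 says fasting may cause fussiness, and the contrast insert in Appendix 3 lists vomiting and diarrhoea as infrequent reactions. The protocol does not give this reason, however, and fasting, contrast and a blood draw recur at Visit 2 (Day 5, give or take a day), which is graded.

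A reader might infer two stronger things. One is that events are lost. They are not: a 6-stool day still counts as diarrhoea, and a Day 0 event is still recorded. The other is that ungraded Day 0 reactions fall mainly in the two arms given injections and so shrink the contrast with and without routine vaccines. The documents give no Day 0 event rates by arm, and the procedures common to all arms that day could equally add noise, so that direction is not supported.

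**Conclusion.** Both inconsistencies are present in section 6.8, and no other section repairs them. Followed literally, the rules leave one stool count and one collection day without a severity grade. The consequence is limited to descriptive summaries by grade of an exploratory outcome, and the number of infants affected cannot be calculated. The primary outcome, terminal ileum thickness on MRI, is untouched. So is the reactogenicity benchmark in Appendix 2, which counts completed assessments rather than grades. The conclusion assumes that the printed inequality is the intended text and that the grading sentence is applied as written. Severity is minor.

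**What to change.** Make two wording edits to section 6.8.

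1. Reconcile the diarrhoea cut-offs so that every count of 3 or more falls in exactly one grade. The sponsor should state whether 6 belongs to Grade 2 or Grade 3; this is a clinical cut-off that the documents do not settle.
2. Align the grading window with the Days 0-14 collection window, and state that Day 0 events are graded when they begin after vaccination. This separates out symptoms already present before the dose, though not later effects of fasting or contrast.

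The cost is small. Stool counts and temperatures are already collected from Day 0, and section 7.3 already records the time of vaccine administration. The memory aid is not reproduced in the documents, so whether it prints grades or records time of onset cannot be checked; if it prints grades, it needs the matching change. Both edits should be made before any data are summarised by grade.
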